The TRS is a multi-item questionnaire capturing 15 symptoms (from PRO-CTCAE) that have been shown to be associated with transplant and general health-related quality of life improvement. These symptoms include change in taste, constipation, diarrhea, swelling in arms or legs, palpitations, dry skin, darkening of skin, blurry vision, headache, insomnia, anxiety, sadness, discouraged, increase in appetite, and fatigue. Each symptom is based on symptom severity in the last 7 days and scaled from 0 (none) – 4 (very severe). Some symptoms also have added questions pertaining to frequency and/or interference with daily activities. The sum of the severity score ranges from 0-60. The improvement in transplant symptoms will be measured by the difference between treatment groups in the mean TRS score.

4. Improvement in health-related quality of life (HRQoL), as measured by the PROMIS-29 health profile, will be compared between groups at 12 months post-kidney transplantation. The PROMIS-29 produces scores for depression, anxiety, fatigue, pain interference, sleep disturbance, physical function, participation in social roles, and pain intensity. Physical and mental health summary scores will also be calculated.

Standardized effect sizes (mean difference / standard deviation) for differences in HRQOL (PROMIS-29) scores will be calculated to compare twice daily immediate release tacrolimus oral to Envarsus XR®.

Clinical Study Protocol [#SIMPLE]

5. Improvement in individual symptoms captured in the TRS questionnaire will be compared.

The standardized effect size (mean difference / standard deviation) on TRS score will be calculated and compared between treatments. Individual TRS items will be classified as improved, worsened, unchanged and compared between treatments.

6. Improvement in overall tolerability or patient bother due to side effects, measured by item GP5 (“I am bothered by side effects of treatment”) from the FACT-G.

Patients’ GP5 responses will be classified as improved, worsened, or unchanged and compared between treatments.

7. Improvement in mean taking adherence, defined as the percent of prescribed doses taken each day (as measured by electronic monitoring), rates between groups.

The assumption is that the mean taking adherence will 75% for the twice-daily immediate release tacrolimus and 90% for the Envarsus XR® (and standard deviations of 38% and 30%, respectively).

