4. PATIENT POPULATION

General Consideration:

The study population is composed of de novo solitary kidney transplant recipients who meet inclusion and exclusion criteria and have not been subject to investigational treatments.

Enrollment Rationale: The Multicenter Transplant Alliance Kidney Consortium collectively transplants more than 1,500 people each year (10% of the total number of kidney transplants in the United States annually). Approximately 60% of these patients will be eligible for this study. We consider a 12 month enrollment time to be a conservative estimate.

Clinical Study Protocol [#SIMPLE]

Screening Failure: Subjects who do not meet the eligibility criteria as outlined below during the screening phase of the study will be considered screening failures.

Inclusion criteria:

Each patient must meet all of the following inclusion criteria to be enrolled in the study:

- Patient is an adult (18 years of age or older).
- Treatment with Envarsus XR® or immediate-release, twice-daily tacrolimus has been indicated by patient's transplant care team.
- Patient is a recipient of a deceased or living donor kidney transplant.
- Patient is able to comply with study procedures for the entire length of the study.
- Patient has been informed about the study survey and has signed an informed consent form.

Exclusion criteria:

Patients meeting any of the following exclusion criteria are not to be enrolled in the study:

- Patient is unable or unwilling to complete study patient reported outcome questionnaires.
- Patient is currently receiving azathioprine
- Patient is currently receiving an mTOR inhibitor (sirolimus, everolimus)
- Patient is currently receiving an belatacept
- Patient has received investigational immunosuppression 1 month prior to transplant or post-transplant
- Patient is in a setting where a professional care taker is responsible for dispensing subject's medication.

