6. NUMBER OF PATIENTS

A total of 240 patients will be enrolled for the study. The enrollment will occur over a 12 month period.

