8. TREATMENT ASSIGNMENT

This is an observational study, and as such, treatment will not be assigned, and there is no intervention. The treatment decision will be made by each patient's transplant care team, independent of the study.

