17. STATISTICAL ANALYSES

Interpretation of scores and score differences in patient-reported measures can be a difficult task since the scales lack the clinical meaning that is inherent in measures of survival, serum concentrations, or anthropometric values. To aid in interpretation of these scores, differences are often standardized by dividing by the standard deviation in the sample to calculate an effect size. There are general guidelines for small, moderate, and large effects on this standardized scale that can be applied to any outcome measure. A standardized effect size (mean difference / standard deviation) less than 0.20 is considered clinically insignificant in the field of patient-reported outcomes research, while effect sizes of 0.30 - 0.40 are generally considered to be minimally important to moderate in magnitude.

For the CIRS, which had a standard deviation of 3.6 in a sample of patients receiving cyclosporine, an effect size of 0.30 corresponds to a difference of 1 point on the 0-20 scale. In the control group, we expect a mean CIRS score similar to or higher than that seen in a sample of patients receiving cyclosporine (3.8 +/- 3.6). A 1 point reduction in the Envarsus XR® group would be equivalent to a 30% reduction in calcineurin inhibitor-related symptoms.

A total of 240 patients will be enrolled. Estimating 15% study dropout provides 204 patients with complete data at the study endpoint, which will allow us to detect effect sizes of 0.28 or larger for the difference between treatment arms with a 2-sided 0.05 level of significance and 80% power in for individual patient reported outcome measure items. This sample size is also appropriately powered to compare adherence rates between groups. Based on assumptions of 75% and 90% mean adherence, respectively, in the 2 groups (and standard deviations of 38% and 30%, respectively), a sample size of 110 per group will yield 90% power to obtain a significant difference between the 2 groups, using a 2-sample t test at a 2-sided 0.05 level of significance.

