For analyses of the CIRS, TRS, and PROMIS-29 scores, we will first calculate change within individuals from enrollment to 12 months. Analysis of covariance (ANCOVA) will be used to compare change between treatments, adjusted for baseline score. The ANCOVA model-estimated mean difference between treatments will be divided by the pooled baseline standard deviation to calculate effect size measures to aid in interpretation. Medication adherence and change in eGFR will be compared between groups using similar models.

For analyses of individual transplant-related symptoms and side effect bother (GP5), within-patient change on each item will be classified as improved, worsened or unchanged and compared between treatments using chi-square tests for ordinal data. Medication satisfaction responses at 12 months will be compared between treatments using an ordinal chi-square test.

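### Medication adherence is planned with unequal SDs and uncontrolled group sizes but no method that tolerates both, and its stated 90% power is not met at the plan's own dropout

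*Combined protocol and SAP*

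**What the plan says.** - **SDs.** Section 3 (Objective and Endpoints), under the adherence endpoint, assumes mean taking adherence of "75% for the twice-daily immediate release tacrolimus and 90% for the Envarsus XR® (and standard deviations of 38% and 30%, respectively". Section 17 (Statistical Analyses) repeats these figures for the sample size.
- **Group sizes.** Section 6 (Number of Patients) fixes only a total: "A total of 240 patients will be enrolled for the study. The enrollment will occur over a 12 month period". Section 8 (Treatment Assignment) says: "This is an observational study, and as such, treatment will not be assigned, and there is no intervention". The care team chooses the formulation. The documents give no ratio, quota or cap.
- **Analysis.** For CIRS, TRS and PROMIS-29, Section 17 says that "Analysis of covariance (ANCOVA) will be used to compare change between treatments, adjusted for baseline score". The same paragraph then says that adherence and eGFR change will be compared by models of the same kind. It names no variance structure, no robust standard error and no check for unequal variances.
- **Power.** Section 17 claims 90% power for adherence at 110 per group, "using a 2-sample t test at a 2-sided 0.05 level of significance". The same paragraph expects 15% dropout from 240, leaving 204 with complete data.

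**The concern.** Ordinary ANCOVA estimates one residual variance for both groups. With equal groups this does little harm even when the true SDs differ. With unequal groups, the pooled variance is weighted towards the larger group. If the larger group is the less variable one, the standard error is too small and intervals are too narrow. If it is the more variable one, they are too wide.

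The plan assumes the more variable group is IR and lets prescribing habit set the split. If XR predominates, a false claim of better adherence on XR becomes more likely than 5%. If IR predominates, a real difference is harder to show. Neither can be known in advance. An uneven split also undermines a power figure stated for two groups of 110.

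**Working it through.** **Inputs.** From the documents: SD 38 (IR) and 30 (XR), difference 90 − 75 = 15 points, two-sided 0.05, 110 per group in the sizing, 240 × 0.85 = 204 completers. Assumed: the splits, and normally distributed data.

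**1. The plan's own figure reproduces.** Average SD = √((38² + 30²)/2) = 34.23. SE = 34.23 × √(2/110) = 4.62. Power ≈ Φ(15/4.62 − 1.96) = 0.901, or 0.899 by the noncentral t. The stated 90% therefore already uses both SDs.

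**2. Dropout.** At 102 per group, SE = √((1444 + 900)/102) = 4.79, and the noncentral t gives 87.6%. Keeping 110 per group would need 220/0.85, or 259 enrolled.

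**3. Pooled against true standard error at 3:1.**
- 153 IR, 51 XR: pooled variance (152 × 1444 + 50 × 900)/202 = 1309.4, so pooled SE = √(1309.4 × (1/153 + 1/51)) = 5.85. True SE = √(1444/153 + 900/51) = 5.20. Intervals are too wide.
- 51 IR, 153 XR: pooled variance (50 × 1444 + 152 × 900)/202 = 1034.7, so pooled SE = 5.20. True SE = √(1444/51 + 900/153) = 5.85. Intervals are too narrow.

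**4. Coverage and power at 204 completers.** Coverage and pooled power come from simulation (400,000 runs per split, no covariate). Welch power comes from the noncentral t. The last column applies one SD of 34.23 to both groups (normal approximation).

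| IR:XR | Pooled coverage | Pooled power | Welch power | Equal-SD power |
|---|---|---|---|---|
| 102:102 | 95.0% | 87.6% | 87.6% | 87.9% |
| 136:68 | 96.6% | 82.6% | 86.3% | 83.9% |
| 68:136 | 93.1% | 84.5% | 80.4% | 83.9% |
| 153:51 | 97.2% | 74.9% | 81.5% | 77.3% |
| 51:153 | 91.9% | 79.0% | 71.6% | 77.3% |

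Type I error is 100% minus coverage, so it runs from 2.8% to 8.1% across these splits. Welch coverage stays between 94.9% and 95.1%.

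**5. Does this carry over to ANCOVA?** With a baseline covariate at an assumed correlation of 0.5, ordinary ANCOVA rejected a true null in 2.7% of runs at 153:51 and 8.0% at 51:153. HC3 errors gave 4.8% at both. Another HC3 simulation gave about 5.4%.

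**6. Source of the power loss.** With equal SDs, 3:1 still lowers power to 77.3%, so imbalance accounts for most of the fall and dropout for the rest. At 51:153 the pooled test looks more powerful than Welch (79.0% against 71.6%) only because its type I error is inflated.

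**The case against.** The strongest reply is that the effect is small and conditional. The SD ratio is 38/30 = 1.27, the endpoint is secondary, and the study is an observational pilot. Coverage is right at 1:1 and misses by about 2 points at 2:1. With 220 completers it drops below 90% only near 9:1 with IR as the small group (22:198, 89.7%). Every unequal split is hypothetical, and a common variance is the usual ANCOVA default, not something the plan states. All of this stands and limits the severity. It does not remove the gap, because the plan itself supplies the unequal SDs and leaves the split open.

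A reader might infer more than the documents support:

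- **That the primary endpoint is affected.** Section 17 gives one CIRS SD, 3.6, and none for XR. A score bounded at 0, with expected mean 3.8 and a hypothesised 30% reduction, could well have a smaller SD on XR. That is plausible but not documented, and residual SDs in a baseline-adjusted change model need not match raw SDs.
- **That t tests are a planned analysis.** The two-sample t test appears only in the sample-size justification.
- **That intervals will be badly wrong.** At the plan's SDs and splits up to 3:1 they are not.
- **That pooling causes the power shortfall, or that robust errors cure it.** Step 6 shows otherwise.
- **That enrolment should be capped at 120 per formulation.** Closing one formulation early in a non-randomised study can make calendar time and site mix differ between groups. It would still leave 102 completers per group. It is also moot on the plan's dates: version 3.0 is dated 8 April 2021 and the last 12-month visit was expected in May 2021.

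**Conclusion.** The point holds for medication adherence, at minor to moderate severity. Under a common residual variance and the plan's SDs, nominal 95% intervals cover about 95% at 1:1, about 93% (XR larger) or 97% (IR larger) at 2:1, and about 92% or 97% at 3:1.

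The power statement is a separate matter. It is arithmetically correct for 110 per group, but the plan's own dropout leaves 102 per group at best, and about 87.6%. Analysed by Welch, it becomes 81.5% at 153 IR to 51 XR and 71.6% at 51 IR to 153 XR.

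These figures rest on the plan's SDs, assumed splits and normal data. Adherence is bounded and probably skewed, so actual behaviour may differ. Section 16 (Criteria for Evaluation) limits adherence measurement to patients able to use the digital system, which could reduce the numbers further.

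**What to change.** 1. **Section 17, analysis.** State that the adherence model will use HC3 standard errors for the treatment difference, its interval and its p-value. Apply the same to the CIRS, TRS, PROMIS-29 and eGFR models as a safeguard. This costs one sentence and one software option, needs no extra patients or data, and changes little if the groups turn out equal. It should be fixed before the outcome data are analysed.
2. **Section 17, power.** Replace the single 90% figure for adherence with power at 204 completers over plausible splits, or at the actual split if enrolment has closed. Use a method that allows unequal variances, and the number of patients expected to have electronic adherence data. This costs a short table. It does not recover the lost power, but it lets readers judge a non-significant adherence result fairly.

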- Adverse Events: During the entire study period, each patient will be monitored at least monthly for trough blood levels, and undergo safety and adverse event assessments as per standard of care. The patient will be followed as appropriate to maintain the tacrolimus trough drug levels of 8 to 10 ng/ml in the first month post-transplant and 6 to 8 ng/ml thereafter.
 - AEs and SAEs will be assigned based on Common Toxicity Criteria for Adverse Events (CTCAE) definitions and tabulated as incidence rates per tacrolimus formulation.
 - Regular monitoring and summaries of hematology, blood chemistries, and urine results.
 - Regular monitoring of vital signs, physical condition, and body weight measurements.
 - Clinically significant infections (confirmed by culture, biopsy, genomic, radiologic, or serologic findings) that requires hospitalization or active anti-microbial treatment will be tabulated as incidence rates per tacrolimus formulation.
 - Cytomegalovirus (CMV), BK Virus, and Epstein-Barr disease will be tabulated as incidence rates per tacrolimus formulation.
 - dnDSA and rejection events are collected as part of standard of care in MTA-K
 - Estimated glomerular filtration rate (eGFR) will be estimated using the MRDR formula.
- Patient-Reported Measures: Patients will complete surveys on their own unless they are unable to. Surveys will be administered electronically so that data will be recorded in the study's database immediately and securely. The following patient reported outcomes measures will be assessed at both study visits.
 - HRQoL: PROMIS -29 profile (29 questions) measuring depression, anxiety, fatigue, pain interference, sleep disturbance, physical function, participation in social roles, and pain intensity
 - Symptoms: Calcineurin-inhibitor related symptoms (5 items) and the Transplant related symptoms (15 items) – items from PRO-CTCAE or in PRO-CTCAE format.
 - Symptoms/Tolerability: FACT- G (GP5) – Single item bothersome assessment (1 question).
- Adherence/Medication Satisfaction Measures: The following adherence tools/measures will be assessed at each study visit throughout the study for those patients capable of using an adherence measurement via a digital capture system:
 - The PROMIS Self-Efficacy for Managing Medication and Treatment (26 questions) – (study visit 1 only).
 - The Transplant Satisfaction Questionnaire for Medication – question 14.

Clinical Study Protocol [#SIMPLE]

Table of Contents

SYNOPSIS.....	3
PROTOCOL	9

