7. STUDY DESIGN

Study Center(s): Multicenter Transplant Alliance – Kidney Centers

Study Design: This is a prospective, multi-center, observational, open-label, study comparing transplant-specific patient reported outcomes and medication adherence between Envarsus XR® and immediate release tacrolimus medication in adult renal transplant recipients. The study will enroll 240 patients and survey these same 240 patients at three time points during the study.

Clinical Study Protocol [#SIMPLE]

Study Design Rationale:

Patients will be enrolled into the study within the first 30 days post-transplant. Treatment will not be determined by this study, and there is no intervention. The treatment decision will be made by each patient's transplant care team, independent of the study.

For the primary objective, comparison of calcineurin inhibitor related symptoms, a standard two-group design will be used to compare treatment groups. These groups will also be compared for transplant-related symptoms, health-related quality of life, adverse events, patient satisfaction, adherence, dnDSA, and graft function.

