14. TIMING OF VISITS

Visit 1: Baseline/Screening

To be collected within the first 30 days post-transplant

- Informed consent
- Demographics
- Medical history
- Complete physical exam including vital signs, height, and weight
- Determination of eligibility based on inclusion/exclusion criteria
- Hematology panel
- Electrolytes including creatinine and eGFR
- Urinalysis
- Baseline Surveys:
 - HRQoL: PROMIS -29 profile (29 questions) measuring depression, anxiety, fatigue, pain interference, sleep disturbance, physical function, participation in social roles, and pain intensity
 - PRO-CTCAE: Calcineurin-inhibitor related symptoms (5 items) and the Transplant related symptoms (14 items)
 - FACT – G (GP5): Single item bothersome assessment (1 question)
 - The PROMIS Self-Efficacy for Managing Medication and Treatment (26 questions) – (study visit 1 only).

Visit 2: Day 120 ± 30 days

All subjects will complete the following prior to morning tacrolimus administration:

- Vital signs, height, and weight
- Hematology panel
- Electrolytes including creatinine and eGFR Tacrolimus trough
- Surveys including:
 - HRQoL: PROMIS -29 profile (29 questions) measuring depression, anxiety, fatigue, pain interference, sleep disturbance, physical function, participation in social roles, and pain intensity
 - PRO-CTCAE: Calcineurin-inhibitor related symptoms (5 items) and the Transplant related symptoms (14 items)
 - FACT – G (GP5): Single item bothersome assessment (1 question)

Visit 3: Day 365 ± 45 days (end of study visit)

All subjects will complete the following prior to morning tacrolimus administration:

- Vital signs, height, and weight
- Hematology panel
- Electrolytes including creatinine and eGFR Tacrolimus trough
- Surveys including:

Clinical Study Protocol [#SIMPLE]

- HRQoL: PROMIS -29 profile (29 questions) measuring depression, anxiety, fatigue, pain interference, sleep disturbance, physical function, participation in social roles, and pain intensity
- PRO-CTCAE: Calcineurin-inhibitor related symptoms (5 items) and the Transplant related symptoms (14 items)
- FACT – G (GP5): Single item bothersome assessment (1 question)
- The Transplant Satisfaction Questionnaire for Medication – question 14.

SCHEDULE OF EVENTS

	Baseline (Within the first 30 days post- transplant)	4 Months Post- Transplant	12 Months Post- Transplant (End of Study)
STUDY VISIT NUMBER	1	2	3
Test/Procedures/Data Collection			
Informed Consent	X		
Review of Inclusion/Exclusion Criteria	X		

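### The eGFR change model takes its baseline from any day in the first 30 after transplant with no term for that day, so unequal enrolment timing could pass for a formulation effect

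*Combined protocol and SAP*

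**What the plan says.** Section 17 (Statistical Analyses) sets out the model for the CIRS, TRS and PROMIS-29 scores: "we will first calculate change within individuals from enrollment to 12 months", and then "Analysis of covariance (ANCOVA) will be used to compare change between treatments, adjusted for baseline score". For graft function it adds only "Medication adherence and change in eGFR will be compared between groups using similar models". It names no covariate other than baseline.

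Section 7 (Study Design) says "Patients will be enrolled into the study within the first 30 days post-transplant". Section 14 (Timing of Visits) lists "Electrolytes including creatinine and eGFR" among the Visit 1 laboratory tests and gives the timing of that visit as "To be collected within the first 30 days post-transplant". No day is fixed. The same tests recur at Visit 2 (day 120 ± 30) and Visit 3 (day 365 ± 45).

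The population is de novo kidney recipients (Section 4). On allocation, Section 8 says "The treatment decision will be made by each patient's transplant care team, independent of the study".

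Section 7 lists graft function among the comparisons between groups. eGFR is also one of the safety labs in the footnote to the Schedule of Events, and changes in safety labs belong to secondary endpoint 10 in Section 3 (item 12 in the Synopsis). The Synopsis adds "Estimated glomerular filtration rate (eGFR) will be estimated using the MRDR formula", which settles neither the reference visit nor the reference day.

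**The concern.** A change score is only as comparable as its starting point. Here one patient's starting eGFR may come from the first days after transplant and another's from day 28. If a new graft's eGFR is still climbing over those weeks, the earlier value is lower and the apparent gain to month 12 larger, even when both patients reach the same function.

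In a randomised trial enrolled before treatment, the day of measurement would balance on average. Here nothing balances it, since formulation is the care team's choice and enrolment may happen at any point in the window. If one group tends to enrol later, it appears to gain less. At stake is the reading of the graft-function comparison: visit timing could be reported as a formulation effect, or could hide a real one.

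**Working it through.** **What there is to reproduce.** The plan states no eGFR effect, SD, power or expected change. The only usable figure is the number of completers: 240 × 0.85 = 204, which agrees with Section 17. That is 102 per group if the groups are equal, which is an assumption because no ratio is stated.

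**Formula.** In an ANCOVA on change adjusted for baseline, the group estimate equals

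(difference in mean 12-month eGFR) − b × (difference in mean baseline eGFR),

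where b is the within-group slope of 12-month on baseline eGFR. With no true effect the first term is zero. If eGFR rises at a given rate per day and the groups' mean enrolment days differ by a gap, the baseline difference is rate × gap. The false difference against the later group is therefore b × rate × gap. An unadjusted change score has b = 1.

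**Linear recovery (all inputs assumed).** By the formula:

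- 0.2 mL/min per day, 2-day gap, b = 0.5: 0.5 × 0.2 × 2 = 0.20
- 0.5 per day, 5-day gap, b = 0.5: 0.5 × 0.5 × 5 = 1.25
- 1.0 per day, 10-day gap, b = 0.5: 0.5 × 1.0 × 10 = 5.0

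Simulation with 102 per group, 3,000 trials, no true effect, true-level SD 13, baseline noise SD 12 and 12-month noise SD 9 gave fitted b of 0.50 to 0.54. Sizes below are against the later group:

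| Rate per day, gap | Planned ANCOVA | False positives | Unadjusted change | False positives |
|---|---|---|---|---|
| 0.2, 2 days | 0.18 | 5.1% | 0.36 | 5.4% |
| 0.5, 5 days | 1.28 | 11.3% | 2.46 | 21.0% |
| 0.5, 10 days | 2.60 | 29.5% | 4.96 | 63.8% |
| 1.0, 10 days | 4.93 | 74.0% | 9.96 | 99.4% |

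With no gap the bias is about 0 and the error rate about 5%. Baseline adjustment roughly halves the false difference but does not remove it.

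**Exponential recovery (all inputs assumed).** Plateau eGFR has mean 58 and SD 16. Visit 1 eGFR = plateau × (1 − exp(−day/τ)) + noise (SD 4), and month 12 = plateau + noise (SD 8). τ is gamma with mean 7 days. Enrolment day is gamma, clipped to days 1-30. There are 102 per group and no true effect. The ranges come from varying the shape of the enrolment-day distribution (gamma shape 2 or 4, with shape 4 for τ):

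| Mean enrolment day | False difference, later group (mL/min) | False positives |
|---|---|---|
| 10 vs 10 | about 0 | 5% |
| 10 vs 12 | about -1.5 (-1.3 to -1.7) | 11% (9-15%) |
| 10 vs 13 | about -2.2 (-1.8 to -2.5) | 18% (13-23%) |
| 8 vs 15 | about -5 (-4.4 to -6.0) | 65-70% (53-82%) |

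**Adding the day of measurement.** Under linear recovery, one term for day brought the bias to between -0.04 and -0.01, with 4.7-5.0% false positives. Under exponential recovery, day alone left up to -2.2 mL/min in an extreme case (mean day 7 vs 21). Day plus log-day gave -0.1 to 0.1 and 4-6%.

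**Dropping the baseline instead.** Take equal enrolment days and a 5 mL/min group difference in underlying function that comes from treatment choice, not from the drug. The unadjusted 12-month comparison passes about -5.1 through, against about -3.0 for the planned ANCOVA.

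**The case against.** The strongest reply is that the two conditions that create the bias are not in the documents. No section says how fast eGFR rises in the first 30 days, and none suggests that enrolment day differs by formulation. This stands, and it is why the point is conditional. With equal enrolment days there is no bias from this source, and with slow recovery and a small gap it is negligible.

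The reading of the eGFR model is also inferred. Section 17 defines change from enrolment only for the three questionnaire scores, and leaves the eGFR reference value to the word similar. That stands too, but it supports clearer wording, since no other reference value is offered.

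A third reply is that eGFR carries little weight: the study is a pilot, eGFR is not named in any numbered endpoint, and no power or decision attaches to it. This is largely fair, although eGFR enters secondary endpoint 10 as a safety lab and graft function is a promised comparison.

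Two stronger inferences are tempting. A reader might conclude that the Visit 1 eGFR mainly reflects the day of enrolment. That follows only from an assumed recovery curve, and partial displacement is all the argument needs. A reader might also conclude that the baseline should be dropped, or replaced by month 4. In a non-randomised study, dropping it passes differences from treatment choice through in full. Month 4 is measured after months of treatment, so adjusting for it conditions on part of any formulation effect.

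**Conclusion.** The structural gap is in the documents: a baseline eGFR from any day in a 30-day window, formulation chosen by the care team, and a model with baseline as its only named covariate. Whether it produces a false difference depends on two things the documents do not state: that eGFR is still rising in the window, and that the groups enrol on different mean days. Under the exponential assumptions, a gap of 2 to 3 days costs about 1.5 to 2.2 mL/min and raises the false-positive rate to about 11-18%. A gap of a week (8 vs 15) costs about 5 mL/min, with 65-70%. At 0.2 mL/min per day and a 2-day gap the error is about 0.2 mL/min and can be ignored.

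The documents do not support saying that the eGFR comparison is biased, only that it is unprotected. Nor does this eGFR point reach the primary CIRS result.

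**What to change.** In Section 17, give eGFR its own sentence in place of the reference to similar models:

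- Name the Visit 1 eGFR as the baseline. Keep it in the ANCOVA and add the post-transplant day of that measurement, as day and log-day, so that non-linear recovery is allowed for.
- Report the 12-month eGFR level by group beside the model result.
- Report the month 4 to month 12 change only as supportive, with a note that month 4 is a post-treatment value.
- Tabulate Visit 1 day by group, so that readers can see whether a gap exists. If the groups' days barely overlap, the adjustment leans on the assumed shape of recovery and should be read with that caution.

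The cost is one or two extra model terms. No new visits, samples or patients are needed: eGFR is already scheduled at all three visits, and the visit windows are counted from transplant. The change does not remove confounding by treatment choice, which needs its own handling.
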